10.54 Second Malignancy

A second malignancy is one unrelated to the treatment of a prior malignancy (and is NOT a metastasis from the initial malignancy). Second malignancies require ONLY routine reporting unless otherwise specified.

10.55 Pregnancy, Fetal Death, and Death Neonatal

If a female subject (or female partner of a male subject) taking investigational product becomes pregnant, the subject taking should notify the Investigator, and the pregnant female should be advised to call her healthcare provider immediately. The patient should have appropriate follow-up as deemed necessary by her physician. If the baby is born with a birth defect or anomaly, a second expedited report is required.

Prior to obtaining private information about a pregnant woman and her infant, the investigator must obtain consent from the pregnant woman and the newborn infant's parent or legal guardian before any data collection can occur. A consent form will need to be submitted to the IRB for these subjects if a pregnancy occurs. If informed consent is not obtained, no information may be collected.

In cases of fetal death, miscarriage or abortion, the mother is the patient. In cases where the child/fetus experiences a serious adverse event other than fetal death, the child/fetus is the patient.

NOTE: When submitting Mayo Expedited Adverse Event Report reports for “Pregnancy”, “Pregnancy loss”, or “Neonatal loss”, the potential risk of exposure of the fetus to the investigational agent(s) or chemotherapy agent(s) should be documented in the “Description of Event” section. Include any available medical documentation. Include this form:

10.551 Pregnancy

Pregnancy should be reported in an expedited manner as **Grade 3 “Pregnancy, puerperium and perinatal conditions - Other (pregnancy)”** under the Pregnancy, puerperium and perinatal conditions SOC. Pregnancy should be followed until the outcome is known.

10.552 Fetal Death

Fetal death is defined in CTCAE as “A disorder characterized by death in utero; failure of the product of conception to show evidence of respiration, heartbeat, or definite movement of a voluntary muscle after expulsion from the uterus, without possibility of resuscitation.”

Any fetal death should be reported expeditiously, as **Grade 4 “Pregnancy, puerperium and perinatal conditions - Other (pregnancy loss)”** under the Pregnancy, puerperium and perinatal conditions SOC.

10.553 Death Neonatal

Neonatal death, defined in CTCAE as “A disorder characterized by cessation of life occurring during the first 28 days of life” that is felt by the investigator to be at least possibly due to the investigational agent/intervention, should be reported expeditiously.

A neonatal death should be reported expeditiously as **Grade 4** **“General disorders and administration - Other (neonatal loss)”** under the General disorders and administration SOC.

10.6 Required Routine Reporting

Neurotoxicity Evaluation to be completed at baseline and each evaluation per NCI-CTCAE v5.0 grading in Appendix VI.

10.61 Baseline and Adverse Events Evaluations

Pretreatment symptoms/conditions do not need to be graded.

10.62 All other AEs

All other AEs will be addressed during the weekly phone calls with the research nurse or clinician. Patient questionnaire booklets are not collected until the end of the study, therefore, will not be used to collect & document AEs.

Submit via appropriate MCCC Case Report Forms (i.e., paper or electronic, as applicable) the following AEs experienced by a patient and not specified in Section 10.6:

10.621 Grade 2 AEs deemed *possibly, probably, or definitely* related to the study treatment or procedure.

10.622 Grade 3 and 4 AEs regardless of attribution to the study treatment or procedure.

10.623 Grade 5 AEs (Deaths)

10.6231 Any death within 30 days of the patient’s last study treatment or procedure regardless of attribution to the study treatment or procedure.

10.6232 Any death more than 30 days after the patient’s last study treatment or procedure that is felt to be at least possibly treatment related must also be submitted as a Grade 5 AE, with a CTCAE type and attribution assigned.

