4.0 Test Schedule

4.1 Test schedule for Chemotherapy-Induced Peripheral Neuropathy

Study Visit	1	2	3	4	5	6	7
Study Time Point	Screening /Baseline (Day -30 to Day 1)	Day 1	End of Week 1	End of Week 2 ^c (+3 Days)	End of Week 3	End of Week 4	End of study
CLINICAL ASSESSMENTS							
Informed consent	X						
Inclusion/exclusion criteria	X ^g						
Demographics/ Medical history	X						
Pregnancy testing ^a	X						
Randomization	X						
Dispense Study Product/Placebo		X		X			
Collect questionnaires							X
Adverse event assessment ^b			X	X	X	X	
STUDY TESTING							
EORTC QLQ-CIPN 20 instrument (Appendix I)	X		X	X	X	X	
Global impression of change (Appendix II)			X	X	X	X	
Chemotherapy Induced Peripheral Neuropathy Assessment Tool (Appendix III)	X		X	X	X	X	
Symptom experience diary (Appendix Va & Vb)	X ^d		X ^e	X ^e	X ^e	X ^e	
NCI-CTCAE neuropathy scale ^f (Appendix VI)	X		X	X	X	X	
Cycle = 14 days							
^a For individuals of childbearing potential. Must be done \leq 7 days prior to registration.							
^b Research nurse or clinician to call patient. Including inquiry about skin toxicity and to assess for suicidal thoughts (Appendix IX). Ask the patient if they have missed any doses of the study							

medication and provide education if necessary. Note any other pertinent information that the patient provides.

^c After subject completes week 2 they will turn in completed questionnaire diary and start the next supply of cream within 1-3 days after completing the first 2 weeks, ideally.

^d Appendix Va: System Experience Diary used for baseline assessment. Must be completed prior to application of study medication.

^e Appendix Vb: System Experience Diary used for weekly assessments. Must be completed at the end of each week.

^f To be completed during research nurse or clinician call to patient per Appendix VI.

^g Required Initial Laboratory Values per inclusion criteria 3.19c can be done any time after the patient has completed their chemotherapy and prior to study registration.

5.0 Stratification Factors:

- Gender (Male, Female, or Other)

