6.4 Baseline symptoms

All required baseline symptoms (see Section 10.6) must be documented and graded.

6.4a Study drug

Study drug is available on site. Each site will have a supply of both investigational product and placebo that will be sent from Nightingale Remedies. After randomization at Mayo, the local site pharmacist will re-label the product per randomization instructions. Research staff, other than pharmacy, are blinded, and will dispense the cream to the patient at the site.

6.4b Patient questionnaire booklets need to be available for patients

Patient questionnaire should be ordered using the Patient Questionnaire Order Form. PDF versions of the questionnaires will be sent electronically for printing.

Patient questionnaire booklets should be provided to the patients. They may be provided to the patient during a routine visit, via mail or electronically. They will be available as follows:

- Questionnaires for Baseline (this should be completed prior to application of study medication)
- Questionnaires for week 1 & 2 (a self-addressed and stamped envelope should be provided the patient to mail this back at the end of week 2)
- Questionnaires for week 3 & 4 (a self-addressed and stamped envelope should be provided the patient to mail this back at the end of week 4)

Before the questionnaires are provided to the patient, the patient initials and appropriate dates of when they are to be completed should be written on each of the questionnaires.

6.4c Study Conduct

The clinical trial will be conducted in compliance with regulations (21 CFR 312, 50, and 56), guidelines for Good Clinical Practice (ICH Guidance E6), and in accordance with general ethical principles outlined in the Declaration of Helsinki; informed consent will be obtained from all participating patients; the protocol and any amendments will be subject to approval by the designated IRB prior to implementation, in accordance with 21 CFR 56.103(a); and subject records will be stored in a secure location and subject confidentiality will be maintained. The investigator will be thoroughly familiar with the appropriate use of the study drug as described in the protocol and Investigator's Brochure. Essential clinical documents will be maintained to demonstrate the validity of the study and the integrity of the data collected. Master files should be established at the beginning of the study, maintained for the duration of the study and retained according to the appropriate regulations.

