16.0 Statistical Considerations and Methodology

16.1 Primary

This is a randomized, two arm, placebo-controlled, double-blind, pilot study of whether CBD can improve CIPN more than a placebo. The purpose of this pilot study is to estimate the treatment effects of CBD compared to the placebo arm. These preliminary efficacy estimates will aid in the design of a large-scale randomized phase III clinical trial.

The primary endpoint is the change in CIPN from baseline to week 2. CIPN will be measured by the sensory subscale of the EORTC QLQ-CIPN20 which is composed of 9 individual items. Secondary endpoints include other measures of neuropathy as measured by the EORTC QLQ CIPN20 motor subscale, the EORTC QLQ CIPN20 autonomic scale, and the CTCAE neuropathy scale. Adverse event profiles will also be assessed using symptom questionnaires and the CTCAE 5.0.

As this is a pilot study, descriptive statistics and statistical plots will be utilized to summarize and estimate the primary and secondary endpoints. Statistical hypothesis testing will be used in an exploratory manner and will be interpreted accordingly.

For the primary analysis, changes in sensory neuropathy from baseline to week 2 will be compared between arms using two-sample, two-sided t-tests. The CBD arm will be compared to the placebo arm. We will construct 95% confidence intervals for the mean difference in sensory neuropathy score between arms. Repeated measures mixed models will be applied to the sensory scores over all time points to determine longitudinal effects and to adjust for confounding factors. Graphical results will include profile plots over time, stream plots of individual changes over time, and forest plots of the 95% confidence intervals by arm.

For logistical and financial reasons, the sample size for this pilot study is set at 40 patients (20 per treatment group). While this is only a descriptive study and is not powered to detect significant differences between arms, the following table provides power analyses for various effect sizes based on a two-sided, two-sample t test at $\alpha = 0.05$ for a fixed sample size of 20 patients per arm.

Effect size, $\Delta = \mu_1 - \mu_2 / \sigma$	0.5	0.6	0.7	0.8	0.9	1.0
Power	0.34	0.46	0.58	0.69	0.79	0.87

For example, we will have 79% power to detect an effect size of 0.9 in EORTC QLQ-CIPN20 with a sample size of 40 patients (20 per arm). This effect size is the mean difference divided by the common standard deviation within each arm.

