17.0 Records and Data Collection Procedures

17.1 Submission Timelines:

Baseline information should be provided within 2 weeks of patient registration, while 2 and 4 week data should be provided within 2 weeks of patient submission of such.

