Appendix IX: Patient Suicidal Thoughts Assessment and Evaluation for Skin Toxicity

Nurse/clinician Phone Call Questions to address regarding suicidal thoughts and potential skin toxicity.

Patients will be asked at the end of each week.

1. Given an abundance of precaution, we want to ask you about whether you have had any thoughts of suicide since starting this protocol?
 - If the answer is 'no', please record.
 - If the answer is 'yes', please record then physician contact is required, and appropriate intervention is to be provided.
2. Do you have skin irritation on your hands and/or feet in the location of the cream application?
3. Do you have any rash, blisters, or open areas of skin in the location of the cream application?
 - Please record responses.
 - If the answer is 'yes' to any of the above two questions, the patient will be asked to come in to be seen by a provider for a skin examination.

Additionally:

4. At the end of weeks 2 and 4, please remind patients to mail in or bring in their questionnaires from the prior 2 weeks.
5. Please note any other pertinent information that the patient provides.

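### Section 10.62 keeps diary-reported side effects out of the adverse event record because booklets supposedly come back only at study end, but four other places have the first booklet back around week 2

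*Combined protocol and SAP*

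**What the plan says.** Section 10.62 makes the telephone call the source of adverse events other than the neurotoxicity grading of section 10.6: "All other AEs will be addressed during the weekly phone calls with the research nurse or clinician". It then excludes the booklets: "Patient questionnaire booklets are not collected until the end of the study, therefore, will not be used to collect & document AEs". In the test schedule (section 4.1), the questionnaire-collection row is ticked only at the end-of-study visit, as far as the extracted table can be read.

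Other places describe an earlier return of the first booklet:

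- Footnote c of the same schedule: "After subject completes week 2 they will turn in completed questionnaire diary".
- Section 6.4b, on the week 1-2 booklet: "a self-addressed and stamped envelope should be provided the patient to mail this back at the end of week 2". A second envelope is provided for weeks 3-4.
- Appendix IX item 4: "At the end of weeks 2 and 4, please remind patients to mail in or bring in their questionnaires from the prior 2 weeks".
- Section 17.1: "2 and 4 week data should be provided within 2 weeks of patient submission of such".

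On use of the questionnaires, section 16.1 says: "Adverse event profiles will also be assessed using symptom questionnaires and the CTCAE 5.0". Section 16.2 compares the incidence and worst value of individual symptom-questionnaire items between arms, by Fisher's exact and Wilcoxon rank-sum tests.

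**The concern.** Evaluating side effects against placebo is the second aim listed under the primary objective (section 2.1). The treatment-period diary (Appendix Vb) asks each week about rash on the hands or feet (item 2), skin side effects of the product (item 4) and any other side effects (item 5). Items 4 and 5 invite a description and severity. Section 10.62 keeps these answers out of the adverse event record for a reason of logistics that most of the relevant passages contradict.

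Two things are at stake. First, a side effect that a patient writes down but does not mention on the call is neither graded nor attributed, and no step compares the two sources. Second, sites have two incompatible instructions on when to collect the booklet that contains the week 2 CIPN20 form, whose sensory subscale is the primary endpoint.

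**Working it through.** No figure in the plan bears on this point, and the power table in section 16.1 is unaffected. The check sets the sections side by side.

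**1. When is the week 1-2 booklet collected?**

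| Place | Timing |
|---|---|
| Section 10.62 | Study end |
| Section 4.1, questionnaire-collection row | Study end (only tick) |
| Section 4.1, footnote c | After week 2, around the change of cream |
| Section 6.4b | Mailed back at the end of week 2 |
| Appendix IX item 4 | Reminder at week 2, and again at week 4 |
| Section 17.1 | Separate week 2 and week 4 data, each due after the patient submits |

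Two places say study end and four point to around week 2. Section 17.1 is the weakest of the four, because it counts from the patient's submission and sets no return date. Section 4.1 contradicts itself.

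**2. Does the exclusion depend on the disputed timing?** Yes. Section 10.62 presents it as a consequence of late collection and gives no other reason. If section 6.4b governs, the stated reason disappears.

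**3. What does the exclusion remove?** Trace a side effect written in the week 1 or week 2 diary:

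- If it is also raised on that week's call, it enters the adverse event record. Nothing is lost.
- If it is not raised, it can still count in the section 16.2 item comparison. It does not become an event graded under section 10.1 and attributed under section 10.3.
- Even if graded, it reaches the case report form only if it meets 10.621 to 10.623: grade 2 and at least possibly related, grade 3 or 4 regardless of attribution, or a qualifying death.

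The events that would change the submitted adverse event data are therefore those written in the diary, not raised on the call, and at or above those thresholds.

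**4. Would the call pick them up anyway?** The Appendix IX script asks about suicidal thoughts, skin irritation, and rash, blisters or open skin. Beyond that, staff note whatever else the patient volunteers. It has no specific question on non-skin side effects, which diary item 5 does ask about.

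**5. Exposure of the primary-endpoint form.** CIPN20 asks about the past week. Section 2.0 plans no washout, and period 2 lasts 14 days. If a site follows the study-end reading, the week 2 form can stay with the patient for at least those 14 days. A form completed late in that interval would describe a week on the other cream. Section 6.4b has staff write the due dates on each form beforehand. The documents describe no record of the actual completion or receipt date, so a late completion might not be seen.

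**6. Upper bounds.** Weekly treatment diaries: 40 × 4 = 160, of which 40 × 2 = 80 belong to weeks 1-2. Week 2 primary-endpoint forms: 40. These are ceilings that assume every site follows the study-end reading. They do not estimate lost events or altered forms, and the documents give no rate from which to estimate either.

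**The case against.** The strongest reply is that this is a drafting inconsistency with little consequence. Much of that reply stands.

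- **Use of the diary data.** A reader might infer from section 10.62 that side effects written down for the first cream are never used. The documents do not support that: sections 16.1 and 16.2 plan to analyse the questionnaire items between arms. Section 10.62 can be read as governing only the adverse event forms, with patient reports as a separate stream, so a conflict with section 16.1 is not inevitable. The plan does not say that this is the intent.
- **The calls.** A reader might infer that the diary is the only place where non-skin side effects are sought. That holds only for scripted wording. Section 4.1 schedules an adverse event assessment at the end of each of weeks 1 to 4, and footnote b does not limit it to skin. Diary and call fall at about the same time each week. Overlap is likely, but the plan does not ensure it.
- **The primary endpoint.** A reader might infer that week 2 data are compromised. They are not shown to be. A site would have to overlook footnote c, the return envelope and the week 2 reminder.
- **Reporting thresholds.** Grade 1 entries, and grade 2 entries judged unrelated or unlikely to be related, would not be submitted even if read on the day of receipt.

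The reply does not remove the contradiction over timing, the missing reconciliation step, or the exclusion's dependence on the disputed timing.

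**Conclusion.** The point holds in limited form and should be fixed. The exclusion in section 10.62 rests on a collection time that four other places contradict. The loss is confined to diary-reported side effects not mentioned on a call, which are never graded or attributed. Only those at or above the section 10.62 thresholds would alter the submitted data. Their number is unknown. The exposure of up to 40 week 2 primary-endpoint forms is a risk that arises only where a site follows the study-end reading. The conclusion assumes that the schedule row has been read correctly from the extracted table, and that no site manual or form outside the supplied documents already sets the collection time or a reconciliation step.

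**What to change.** 1. Set one collection schedule, the end of weeks 2 and 4, in the section 4.1 row and footnote c, section 6.4b, section 10.62, section 17.1 and Appendix IX. Move the tick in the schedule row accordingly.
2. Delete the clause in section 10.62 that bars the booklets from adverse event documentation.
3. Add a step on receipt of each booklet: compare Appendix Vb items 2, 4 and 5 with that week's call record. Grade any event not already recorded under section 10.1 and attribute it under section 10.3. Submit it if it meets 10.621 to 10.623, with the treatment period recorded. Recording period 1 or 2, not the cream, keeps staff blinded.
4. State that lower-grade entries stay in the section 16.2 item analysis, so that the two streams are distinct.
5. Record the actual completion and receipt dates of the week 1-2 booklet.

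The cost is a wording change plus a few minutes of staff review for each of at most 40 × 2 = 80 returned booklets. The envelopes and reminders are already planned.

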10.7 Late Occurring Adverse Events

Refer to the instructions in the Forms Packet (or electronic data entry screens, as applicable) regarding the submission of late occurring AEs following completion of the Active Monitoring Phase (i.e., compliance with Test Schedule in Section 4.0).

10.8 Deviation Reporting Instructions

For Non-MCCC institutions All deviations must be reported in the Medidata Rave® EDC system via appropriate Case Report Forms. Mayo Clinic Cancer Center (MCCC) Institutions will report via institutional standards.

11.0 Treatment Evaluation/Measurement of Effect

See statistical details in Section 16.

12.0 Descriptive Factors: Not applicable.**13.0 Treatment/Follow-up Decision at Evaluation of Patient**

Physicians can use the unblinded study data, for the individual patient, to help determine subsequent therapy for individual patients.

14.0 Body Fluid Biospecimens – None.**15.0 Drug Information**

Placebo and creams will be provided by Nightingale Remedies. This product has been tested by an independent lab for content and has 0% THC (testing attached). The study cream contains CBD isolate; both creams are odorless. 4-5 pumps of product will cover hands/feet and contains approximately 4 mg of CBD isolate. Patients with CIPN only on hands or feet would then get approximately 8 mg of topical CBD per day. Patients with CIPN on both locations would get approximately 16 mg of topical CBD per day. See appendix VII for product ingredients. See investigator brochure for detailed information about drug product and safety issues.

[figure not shown]
Shipping, handling, and storage

Creams should be stored at room temperature (59°-77°F). Product will be shipped from Nightingale Remedies to participating sites. They will not be blinded to their local pharmacist who must keep all of the other clinical partners blinded to the study product and placebo.

IND number: 157457

15.1 CBD Cream**15.11 Drug procurement:**

Nightingale Remedies will supply all drug. Each institution will order the drug from Nightingale Remedies. Submit the Drug Order Form request to:

Outdated or remaining drug is to be destroyed on-site per procedures in place at each institution.

The investigator is responsible to ensure supervision of accurate monitoring of the receipt, storage and allocation of the study product. Copies of all invoices of shipments must be retained. Accurate study product inventory, dispensing and accountability logs must be obtained and stored in the Pharmacy Binder.

15.111 Each participating institution may ship Study Product/Placebo directly to their patients if the site standards allow. All local site procedures should be followed and accurate accountability logs should be maintained.

